REACH (Rehabilitation Enhancing Aging through Connected Health): Detailed Protocol

III. SUBJECT SELECTION

This proof of concept quasi-experimental pilot study will evaluate the benefit of a novel rehabilitative care program on physical function and health care utilization after one year of follow up. We will recruit 76 community dwelling older adult primary care patients.

Inclusion criteria:

1. Age \geq 65-95 years
2. Able to understand and communicate in English
3. Difficulty or task modification with walking $\frac{1}{2}$ mile (6 blocks) or climbing one flight of stairs
4. Ability to continuously walk 400 m in less than 15 minutes without stopping for more than a minute at a time, sitting, leaning, or the help of another person
5. Lives in a zip code within 10 mile radius of Spaulding Cambridge Facility
6. Baseline Short Physical Performance Battery (SPPB) scores from 3-12 with <20% of SPPB scores in the 11-12 range

Exclusion Criteria:

1. Presence of a terminal disease (e.g. receiving hospice services, metastatic cancer)
2. Major surgery or Myocardial Infarction in the last 6 months
3. Planned major surgery (e.g. joint replacement)
4. Planned move from the Boston area within 1.5 years
5. Mini-mental state exam (MMSE) score <20
6. Major medical problems interfering with safe and successful testing (examples may include: history hip replacement with recurrent dislocation, uncontrolled hypertension, use of supplemental oxygen)

Recruitment procedures will follow the same methodology utilized within the previously IRB approved Boston RISE cohort study.⁷ Prior to contacting any potential participants, [name] and his staff will convene educational sessions with clinicians from participating primary care practices at Mass General Hospital in order to familiarize their staff with the study. To facilitate continued and regular support with recruitment throughout the course of the study, [name] and his research coordinator at MGH primary care are collaborators. They will facilitate recruitment from primary care clinics within the MGH healthcare systems.

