The target of the primary care-based recruitment will be adults aged 65 to 95 receiving primary care within clinics of the MGH, representing a diverse population of older adults. Recruitment will *not* specifically target primary care patients who have been referred to physical therapy for treatment of a specific condition that they manifest such as a knee injury. Rather, it is targeting older adults in need of preventative care, which is a novel focus for rehabilitation. Potential participants will be identified through the MGH Primary Care Operations Improvement (PCOI) loyalty cohort (Protocol # 2004P002796) and direct identification by cooperating primary care providers. This patient database (Primary Care Provider Loyalty Cohort, IRB: 2004P002796) is stored on a password-protected server at the MGH Laboratory of Computer Science. At all times, data and results will be protected in conformance with the confidentiality policies of the Massachusetts General Hospital, the security procedures of the Laboratory of Computer Science, and the

REACH (Rehabilitation Enhancing Aging through Connected Health): Detailed Protocol

applicable policies of Partners Information Systems. Upon receipt of IRB approval, this patient database will be securely imported into the established REDCap tracking database by [name] and his team at MGH.

Once in REDCap, this recruitment database will be accessed initially to provide MGH primary care physicians with the names of their patients so that they can corroborate an individual's eligibility and designate those to whom they feel that letters should be sent. Study ID's will be assigned to the remaining potential participants and recruitment letters will be mailed. We may access the recruitment database during the course of the study for the following purposes:

- To contact participants for payment and study-related issues
- To inform design for future studies that may result from this study
- For mandated reporting from the funding agency

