data, including Medicare claims. Brandeis has a long standing relationship with the Center for Medicaid and Medicare Services and houses a large volume of administrative claims that are used for a variety of evaluation and development activities.

We will not be recruiting a control group, but selecting a matched group of participants from the Boston RISE cohort study as controls for aim 1, which focuses on functional outcome measures. The Boston RISE cohort study is a longitudinal cohort study evaluating mobility decline among older primary care patients. Boston RISE contains all of the primary and secondary outcome measures of the study. For outcomes utilizing Medicare Claims data, data is only available for a geographic region encompassing a minimum of 250,000 individuals. Thus, for aims 2 and 3, our collaborators at Brandeis will also identify a second matched control group based upon scientifically relevant data elements, such as age, gender, race, chronic conditions, etc.

VI. BIOSTATISTICAL ANALYSIS

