This quasi-experimental study will use a difference-in-difference (D-in-D) approach to assess the impact of mHealth supported PT compared to treatment as usual. We will use a strong matching algorithm, such as exact matching on age, sex and the propensity to participate in treatment, to ensure comparability on observable characteristics between treatments and control group members. For this study the propensity score serves as a form of data reduction, taking many diagnostic flags and reducing them to a single covariate. The basic model estimates the effect of treatment on the change in outcome between baseline and follow-up: $y_{it} = \beta_0 + \beta_1 treatment_i + \beta_2 post_{it} + \beta_3 treatment_i * post_{it} + \gamma controls_{it} + \alpha_i + \varepsilon_{it}$ where y_{it} is cost, $\gamma controls_{it}$ are patient socio-demographic characteristics and $treatment_i$ is a 0/1 variable indicating treatment status. β_3 is the parameter of interest, capturing the joint effect of being in the treatment group at time 2. For the first study object, this model can be extended to include repeated measures of functional status over time. This is a proof of concept pilot study and thus we may not be powered to observe statistically significant differences among our outcomes between groups. However, the effect sizes will be utilized to inform the design of larger trials. For example, meaningful differences in the LLFDI have been published by our group and will help interpret the magnitude of treatment effects observed.

VII. RISKS AND DISCOMFORTS

Common risks and discomforts

All of the proposed measures have been validated among older adults of varying health status. The staff has extensive experience conducting these measures safely among older adults with mobility problems. Many of the assessments for this study involve minimal risk to the participants such as questionnaires, measures of leg strength and power using a double leg press machine, measurement of core muscle weakness, performance of simple balance testing, standing up from a chair, walking eight feet, and balancing with feet in a tandem position. Thus the risks are expected to be similar to those risks involved in participating in a physical therapy program, standing, stair climbing, walking, and activities of daily living. The balance and walk tests could potentially result in a fall, but the protocol includes careful personal monitoring during the

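### The only matching rule the plan names, given as an example, could leave most of the 76 participants unmatched for Aim 1 if applied literally in a cohort-sized pool such as Boston RISE

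*Combined protocol and SAP*

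**What the plan says.** Section III sets the treated group: "We will recruit 76 community dwelling older adult primary care patients", drawn from "adults aged 65 to 95 receiving primary care within clinics of the MGH". Section V says that no controls will be recruited. For functional outcomes the investigators will be "selecting a matched group of participants from the Boston RISE cohort study as controls for aim 1". For utilisation and cost, Medicare "data is only available for a geographic region encompassing a minimum of 250,000 individuals", and the collaborators will "identify a second matched control group based upon scientifically relevant data elements, such as age, gender, race, chronic conditions, etc".

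The method of matching appears only in Section VI, which promises a strong algorithm and offers, as an example, "exact matching on age, sex and the propensity to participate in treatment". The same paragraph adds that "the propensity score serves as a form of data reduction, taking many diagnostic flags and reducing them to a single covariate".

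The documents do not state the size of the Boston RISE pool, the number of flags, the unit in which age is matched, any tolerance on the score, the control-to-participant ratio, whether controls may be reused, or what happens to a participant with no match. They also do not say whether the Section VI example is meant for both control groups.

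**The concern.** The study is not randomised, so matching is a main protection against differences between participants and controls. Exact matching on a propensity score works against the purpose of the score. Two people share a score only if they share a flag pattern (chance coincidences aside), and the number of patterns doubles with each flag. Requiring exact age as well splits a modest cohort into many small cells before the score is considered.

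If most of the 76 have no match, a matched Aim 1 comparison describes an unplanned subset and loses precision. Section VI intends the effect sizes to inform larger trials, so an estimate from such a subset would carry forward. If the rule is relaxed instead, the tolerance decides who is compared with whom, and the plan does not fix it. Section I describes Boston RISE as the same group's own cohort, so control outcomes may already be to hand when that choice is made.

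**Working it through.** The plan gives no match rate or matched sample size, so there is no figure to reproduce. The check asks how many of 76 would be matched under each reading of the rule.

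**From the documents.** 76 participants; ages 65 to 95; two sexes; a score from many binary flags.

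**Assumed, because the documents are silent.** Aim 1 pool of 200, 400 or 1,000; 5 to 20 flags; age in whole years, centred near 75; about 65% women; independent flags with prevalence 5–50%; log-odds coefficients with SD 0.3; 1:1 matching without reuse.

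**Cell counts.** Single-year age by sex gives 31 × 2 = 62 cells. The average number of controls per cell is 200/62 = 3.2, 400/62 = 6.5 or 1,000/62 = 16.1. The number of possible flag patterns is 2^5 = 32, 2^10 = 1,024 or 2^20 = 1,048,576. With 5 flags a tie within a cell is plausible; with 20 it is not.

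**Simulation.** Mean number matched of 76 (100, 100 and 60 replicates for the three pools):

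| Rule | Pool 200 | Pool 400 | Pool 1,000 |
|---|---|---|---|
| Exact age and sex only (10 flags) | 67.9 | 74.2 | 75.7 |
| Plus identical score, 5 flags | 22.0 | 35.5 | 52.7 |
| Plus identical score, 10 flags | 3.4 | 6.6 | 14.1 |
| Plus identical score, 15 flags | 0.4 | 0.6 | 1.5 |
| Plus identical score, 20 flags | 0.1 | 0.1 | 0.2 |
| Plus score equal to 2 decimals, 10 flags | 13.1 | 29.2 | 58.0 |
| Plus 0.2 SD logit caliper, 5 flags | 34.6 | 49.3 | 64.9 |
| Plus 0.2 SD logit caliper, 10 flags | 27.0 | 41.7 | 60.9 |
| Plus 0.2 SD logit caliper, 20 flags | 26.7 | 39.5 | 59.5 |

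Repeat simulations agree closely. One gave 22–50 at 5 flags, 3–11 at 10, about 0 at 20, and 27–64 for the caliper with exact age. Another gave 3.5, 6.5 and 15 at 10 flags. The upper ends, about 50–53 at 5 flags and 11–15 at 10, should be read as approximate.

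Exact age and sex alone match 68 or more, so the loss comes from adding the score. A caliper recovers only part of it while age stays exact.

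**Relaxing age.** With the same caliper, sex exact and age within 3 years, the number matched at 10–20 flags was 60–62, 69–71 and about 74 for the three pools. The repeat run gave about 62–75 across the pools. That leaves roughly 76 − 75 = 1 to 76 − 62 = 14 unmatched.

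**Claims pool (Aims 2 and 3).** With an assumed 250,000 controls, the identical-score rule matched 74 at 10 flags, 51 at 15 and 26 at 20. With the score rounded to 2 decimals, about 76 matched at pools of 30,000 or more. These largest pools used only 6 and 2 replicates, so the figures are indicative.

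**Several controls per participant.** With equal variances and independent controls, the standard error of k:1 relative to 1:1 is √((1 + 1/k)/2). At k = 5 this is √(1.2/2) = 0.775, a reduction of about 23%.

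**The case against.** The plan offers the rule as an example of strong matching and does not commit to it. The phrase can also be read as exact on age and sex with some unspecified form of score matching. Both points stand, and they limit the conclusion to what follows if the example is applied as written. It remains the only rule named, and a common caliper with exact age still leaves many participants unmatched in the smaller pools.

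A reader might infer that the method cannot be carried out at all. The documents do not support that. A score made only of binary flags is discrete and can tie; with few flags or a very large pool many participants match, and a rounded or stratified score is workable. A simulation with a continuous covariate in the score would show no exact matches, but only by construction, and the plan describes flags. Conversely, many flags points towards the low-yield rows of the table.

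A reader might also extend the problem to all three aims. The claims region covers at least 250,000 individuals, although the number of usable controls is not given. Section V's list of matching variables for that group does not mention the score.

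Finally, nothing in the plan says that unmatched participants will be dropped or that a tolerance will be chosen after outcomes are seen. It is silent on both, so these are open risks and not stated procedures. The Section VI model also has socio-demographic covariates and a person term, so matching is not the only control for imbalance. The study is a pilot that disclaims power, which lowers the stakes but does not remove the need for an interpretable comparison.

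**Conclusion.** The concern holds for Aim 1 in conditional form. If the named example is applied literally to a score from 10 or more flags, in a pool of 200 to 1,000, it matches at most about 15 of 76, and about none at 20 flags. With 5 flags it matches about 22 to 50. A 0.2 SD logit caliper with exact age matches about 27 to 64.

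These figures rest on assumed pool sizes, flag counts and flag distributions. Correlated flags would produce more ties; finer age units or any continuous covariate in the score would produce fewer. For Aims 2 and 3 the difficulty is much smaller if the claims pool is very large.

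This goes beyond missing detail, because the one rule offered performs poorly where a standard alternative performs well. It should be changed before analysis. It does not show that the design is unworkable.

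**What to change.** For Aim 1, replace the example in Section VI with nearest-neighbour matching on the logit of the propensity score, caliper 0.2 SD, exact on sex and within 3 years of age, and keep age as a covariate in the outcome model. The caliper and age window are conventions; what matters is that they are written down.

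For each control group, list the covariates in the score and state the ratio, whether controls are reused, and how unmatched participants are handled. Fix the rule before outcomes are merged. Report standardised differences after matching and the number unmatched.

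In the claims pool, draw up to 5 controls per participant, for the gain in precision shown above.

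The cost is protocol wording and routine matching code. The downside is small residual age differences within pairs, which the age covariate addresses, and some participants may still be unmatched, mainly if the Boston RISE pool is near the low end of the assumed range.

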The exercises are based upon standard rehabilitative techniques advocated for older adults. They will address attributes known to impact mobility such as leg strength, leg speed, trunk muscle endurance, limb flexibility, postural stability and cardiovascular endurance. Exercise specifics will target upright functional movements with progressive levels of difficulty and intensity with the goal of providing a safe, robust stimulus that is acceptable and most likely to produce improved function. A variety of exercises are included to guard against adaptation or boredom over the 12 month study. The exercises will utilize limited equipment and lend themselves to safe, independent performance in the home environment. See attachment, "Sample Exercises for REACH Study". Each patient will be assigned up to seven exercises at any given time. Exercises will be progressed or modified in response to participant feedback. In addition, the participants will be instructed in a progressive walking program that will be monitored via participant report relative to the frequency and time spent in the activity. The uniqueness of this interventional protocol lies in the method of physical therapy delivery: 1) limited face to face treatment sessions spaced over a longer period of time 2) remote monitoring for an extended period 3) enhanced exercise performance with provision of videos/communications via the Wellpepper application.

As mentioned in our "*Background and Significance*", our collaborators at Brandeis have evaluated health care utilization in many studies, including cardiac and vision studies. They will utilize similar methodology and access the Medicare claims data for all of our participants. More details about their data access and management are provided later within the "*Monitoring and Quality Assurance*" section. The claims data requested will include the one year time period during which the participant is active in the study as well as the 6 months following their one-year assessment. The additional 6 months allows for an appropriate "run-out" to account for the discrepancies between when health care utilization (such as an Emergency Room visit) occurs versus when the event appears in the claims data. The Heller School at Brandeis University has developed a comprehensive information security policy and built a secure data network to house sensitive

REACH (Rehabilitation Enhancing Aging through Connected Health): Detailed Protocol

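### The protocol states no pre-enrolment claims window and does not date the diagnostic flags used to match Aim 2 and 3 controls; flags taken from the stated window would be post-treatment

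*Combined protocol and SAP*

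**What the plan says.** **Claims window (Section V, Study Procedures).** "The claims data requested will include the one year time period during which the participant is active in the study". The request then extends for a further half-year beyond the 12-month visit, and that extension is explained as run-out for claims that appear late. No look-back before enrolment is mentioned here or elsewhere.

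**Aim 2 and 3 controls (end of Section V).** The claims analysis group will "identify a second matched control group based upon scientifically relevant data elements, such as age, gender, race, chronic conditions, etc". No measurement date is given.

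**Matching and model (Section VI, Biostatistical Analysis).** The matching is described by example, as "exact matching on age, sex and the propensity to participate in treatment", and "the propensity score serves as a form of data reduction, taking many diagnostic flags and reducing them to a single covariate". Neither the source nor the dates of the flags are stated. On the estimator: "The basic model estimates the effect of treatment on the change in outcome between baseline and follow-up".

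**Outcomes (Section II, Specific Aims).** Aim 2 concerns hospitalizations and ED visits, and Aim 3 health care costs, each over one year of follow-up.

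**The concern.** A matching variable should be fixed before treatment can influence it. Diagnosis codes are produced by health care encounters, and admissions and ED visits are the encounters that Aim 2 counts and Aim 3 prices. If the flags are read from claims of the on-study year, matching holds constant part of what the programme is meant to change.

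The bias can go either way:

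- If the programme prevents admissions, participants collect fewer new codes and are paired with controls who also had few admissions. The effect shrinks.
- If existing conditions are coded more fully in one group than in the other during that year, people with the same flags differ in true illness. That can look like a saving or an excess when there is neither.

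Section VI says that the effect sizes will inform larger trials, so a biased estimate matters even in a pilot that may lack power.

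**Working it through.** The protocol states no figure to reproduce on this point. The check has a textual part and an illustrative part.

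**1. Pre-enrolment months in the stated window.** On-study year: months 0 to 12. Run-out: months 12 to 18. Pre-enrolment months: 0.

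**2. Where the flags could come from.** The comorbidity questionnaire in Section V is given to enrolled participants. Nothing says that the Medicare controls have it, and claims are the only data source described for them. Flags comparable across both groups would therefore have to come from claims, and the only claims with stated dates are those in step 1.

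**3. Illustration for cost.** None of these inputs is from the documents.

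- Prevalent condition C: 35% of participants, 30% of controls.
- New diagnosis D in the year: 10%, or 20% in people with C.
- C and D each add 1 SD to cost.
- The on-study flag F is 1 if C is coded in the year or D occurs.
- The estimate is the participant-minus-control cost difference within levels of F, weighted to participants.

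*(a) True effect, C fully coded.* The programme halves D and acts only through D.

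- Truth: 0.10 × (0.5 − 1) × (1 + 0.35) = −0.0675 SD.
- Matching on C before enrolment: 0.35 × (−0.10) + 0.65 × (−0.05) = −0.0675. The truth is recovered.
- Matching on F, participants: P(F=1) = 0.35 + 0.65 × 0.05 = 0.3825. Mean cost given F=1 is (0.35 + 0.0675)/0.3825 = 1.0915, because P(D) = 0.35 × 0.10 + 0.65 × 0.05 = 0.0675.
- Matching on F, controls: P(F=1) = 0.30 + 0.70 × 0.10 = 0.37. Mean cost given F=1 is (0.30 + 0.13)/0.37 = 1.1622, because P(D) = 0.30 × 0.20 + 0.70 × 0.10 = 0.13.
- With F=0 neither group has C or D, so the difference is 0.
- Estimate: 0.3825 × (1.0915 − 1.1622) = −0.027, which is 40% of the truth.
- Matching on C and D as separate flags gives 0, since the whole effect runs through D.

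*(b) No true effect, fuller coding of C in participants (0.85 against 0.70).*

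- Participants: P(C, F=1) = 0.35 × (1 − 0.15 × 0.80) = 0.308. P(F=1) = 0.308 + 0.065 = 0.373. P(D) = 0.135. Mean given F=1: (0.308 + 0.135)/0.373 = 1.188. Mean given F=0: 0.042/0.627 = 0.067.
- Controls: P(C, F=1) = 0.30 × (1 − 0.30 × 0.80) = 0.228. P(F=1) = 0.228 + 0.07 = 0.298. Mean given F=1: (0.228 + 0.13)/0.298 = 1.201. Mean given F=0: 0.072/0.702 = 0.103.
- Estimate: 0.373 × (−0.0137) + 0.627 × (−0.0356) = −0.027, a false saving.

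A simulation of 2,000,000 people agreed (−0.027 and −0.028) and covered further cases:

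| Case | Truth | Pre-enrolment flag | On-study flags |
|---|---|---|---|
| No effect, coding 0.70 in both | 0 | −0.001 | +0.02 |
| No effect, coding 0.85 v 0.70 | 0 | −0.001 | −0.03 |
| No effect, coding 0.55 v 0.70 | 0 | −0.002 | +0.06 |
| D halved, full coding | −0.068 | −0.068 | −0.03 to 0.00 |
| D halved, coding 0.70 in both | −0.068 | −0.066 | 0.00 to +0.03 |

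Ranges run from one combined flag to separate flags for C and D.

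**4. Illustration for admissions.** A second simulation assumed a mean of 3 prior flags, 0.25 admissions per person-year, 0.3 background new flags, and 0.5, 1 or 2 new flags per admission.

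- True rate ratio 0.70: matching on prior plus on-study flags gave 0.716, 0.724 and 0.782.
- No effect, with 0.3 extra coded flags per participant: about 0.89.
- Varying the assumed link between prior flags and admissions widened these to 0.70 to 0.79 and 0.87 to 0.93. Matching on prior flags stayed within 0.03 of the truth.

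**5. The estimator.** With on-study rows only, post is always 1 and treatment × post equals treatment. The four-column design of intercept, treatment, post and interaction then has rank 2, and β₃ cannot be estimated. With pre- and post-enrolment rows it has rank 4.

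**The case against.** **Two stronger readings that a reader might infer.** One is that only post-enrolment claims will be obtained. Section V says what the request will include, not that it is limited to this. The other is that the flags are post-treatment as a matter of fact. The protocol neither sources nor dates them, and a propensity to participate, like a change from baseline, is naturally a pre-treatment notion. Section V also says that the claims group holds other claims. All of this stands, and it makes the point conditional. It does not supply a window: the years and role of those other claims are not given, and Section IX says that the data use agreement confines the team to the project described in the Privacy Board packet. A baseline period for the outcome would also not settle when the matching flags are measured.

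**On the size.** Neither simulation is the planned analysis. Both match on flags directly, without an estimated propensity score or a difference-in-difference. At 0.5 flags per admission the attenuation (0.716 against 0.70) is negligible, and even 0.782 keeps ln 0.782 / ln 0.70 = 69% of the log effect. With 76 participants at the assumed rate, 76 × 0.25 × 0.70 = 13.3 admissions are expected. The standard error of the log rate ratio is then about 1/√13.3 = 0.27 even with unlimited controls, so this bias is ln(0.716/0.70)/0.27 = 0.08 to ln(0.782/0.70)/0.27 = 0.4 standard errors. This stands. Random error would dominate in the pilot, and the figures show direction and possibility only.

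**On extra coding.** A reader might take the referral to primary care in Section VII as evidence that participants will be coded more. It covers only participants with adverse events, in a section that calls the listed serious events very unlikely. It does not support a general coding difference.

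**On the covariates.** Section VI already limits the model controls to socio-demographic characteristics, so the point concerns matching alone.

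**Conclusion.** The point holds in conditional form. The only stated claims window contains no time before enrolment, and nothing dates the conditions and flags used to match the Aim 2 and 3 controls. If they are taken from that window, they are post-treatment and partly generated by the Aim 2 outcome, and both aims can be biased in either direction. Nothing in the protocol prevents this.

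The documents do not fix the size. The illustrations run from negligible to a hidden or reversed effect, and they rest wholly on assumed prevalence, incidence and coding. This is worth correcting before the claims are requested, because flags cannot be restricted to dates for which no claims are held.

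**What to change.** - **Section V, claims request.** Add a pre-enrolment look-back, for example 12 months, for participants and controls alike.
- **Section VI, matching.** State that every claims-based variable used for matching or in the propensity score, including chronic conditions and diagnostic flags, is computed only from claims dated before the participant's enrolment date, or before a corresponding assigned index date for controls. State how that index date is assigned.

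Both parts are needed. The rule cannot be applied without the earlier claims, and the earlier claims do not help if flags may still be drawn from the on-study year.

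The cost is a sentence in each section, a date filter in the claims program, a somewhat larger claims request and the possible loss of people without full look-back coverage. The same look-back supplies the baseline period for cost and utilization that the difference-in-difference model needs.
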